- w: Two plasma PK samples will be obtained: 1 sample at predose (trough) and another sample 1 to 6 hours postdose at Visits 3, 4, 6, 7, 9, and 11 and another sample 4 to 8 hours postdose at Visit 13 (or ED). Therefore, subjects or their study partners must be instructed not to take their study drug at home on the day the PK sampling is performed. Instead, subjects will take the study drug at the clinic after collection of the predose PK sample. At Visit 13 (or ED), the trough PK blood sample should be collected shortly before or after completing the LP for subjects participating in the CSF substudy. If the study drug is temporarily suspended, postdose PK samples will not be required. If at an ED Visit, the subject has already stopped study drug, postdose

Table 5 Schedule of Procedures/Assessments in Study E2609-G000-302 (Revised per Amendments 04 and 05)

Phase Period	Randomization														Follow-Up		UNS Visit ^d
	Treatment												ED ^b	14 ^c	15 ^c		
Visit ^a	2	3	4	5	6	7	8	9	10	11	12	13	ED ^b	14 ^c	15 ^c		
Day	1	15	29	57	85	183	274	365	456	547	638	729		757	813		
Week	1	3	5	9	13	27	40	53	66	79	92	105		109	117		
Weeks elapsed since 1st dose	0	2	4	8	12	26	39	52	65	78	91	104		108	116		
Nominal months elapsed since 1st dose	0		1	2	3	6	9	12	15	18	21	24		25	27		
Procedures/ Assessments																	

PK samples are not required.

- x: PD and exploratory biomarker blood samples should be collected at fasting or at least 2 hours after the most recent meal and, as far as is feasible, samples should be taken at the same time of day at all visits. Samples should be taken predose at Visits 2, 3, 4, 6, 7, 9, 11, 13 (or ED), 14, and 15. (revised per Amendments 02 and 03)

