- y: For subjects who consent to participate in the CSF longitudinal substudy. Visit 13 (or ED) also includes blood PK and PD assessments and so the subject will be dosed at the clinic on these days. A CSF sample will be collected by LP between 4 and 8 hours postdose and at the same time of day as the subject's Screening LP (±1 hour). The CSF sample will be taken with the subject fasting (preferred) or at least 2 hours after the most recent meal. A gravity drip collection method must be used. If performed on the same day as the cognitive tests, the LP will be performed after the cognitive tests; the subject should rest and drink some fluid to hydrate after the cognitive tests and before the LP. Subjects will be encouraged to stay at the site after completion of LP for medical observation. The CSF sample will not be taken at the ED Visit if this visit occurs within 39 weeks of treatment or 3 months of a previous CSF sample. If at an ED Visit, the subject has already stopped study drug, then no dosing will take place, but the CSF sample will still be collected unless it was already collected within the past 3 months. Subjects receiving concomitant anticoagulation/antiplatelet therapy should have prothrombin time and INR (derived from prothrombin time) before LP; if they are assessed by the investigator to be at risk for bleeding, they are to be excluded from CSF collection. Note that subjects who are assessed by both amyloid PET and CSF are required to wait for a minimum of 48 hours between the 2 procedures. (revised per Amendment 01)
- z: Subjects reporting AEs relating to abnormal dreams, nightmares, or sleep terror will be questioned on the nature, frequency, and impact of these events.
- aa: AEs that may signal drug abuse potential require a more detailed follow-up through completion of a specific eCRF form (Possible drug abuse potential form/ questionnaire). Similarly, AEs reported during the first 4 weeks following the last dose of study drug that might indicate physical dependency also require a more detailed follow-up through completion of the same eCRF form. Categories and examples of AEs indicating signals of possible drug abuse are provided in [Appendix 3](#) and a more comprehensive list is provided in the eCRF Completion Guidelines. (revised per Amendments 01 and 03)

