- ^v Site staff will contact the subject or the study partner the day before the PK blood sampling to provide instructions that subjects must not take their study drug at home on the day of the PK blood sampling. During this telephone contact with the subject or the study partner, the site staff should document the time that the subject took their study drug that day, ie, the day before the PK blood sampling.
- ^w Two plasma PK samples will be obtained: 1 sample at predose (trough) and another sample 1 to 6 hours postdose at Visits 3, 4, 6, 7, 9, and 11 and another sample 4 to 8 hours postdose at Visit 13 (or ED). Therefore, subjects or their study partners must be instructed not to take their study drug at home on the day the PK sampling is performed. Instead, subjects will take the study drug at the clinic after collection of the predose PK sample. At Visit 13 (or ED) the PK blood sample should be collected shortly before or after completing the LP for subjects participating in the CSF substudy. If at an ED Visit, the subject has already stopped study drug, then no dosing will take place, but the trough PK sample will still be collected. For subjects participating in the CSF substudy who have stopped taking study drug prior to the ED visit, the LP should be performed at approximately the same time as at the Screening Visit, and then a trough PK sample will be collected either shortly before or shortly after the LP.
- ^x PD and exploratory biomarker blood samples should be collected at fasting or at least 2 hours after the most recent meal and, as far as is feasible, samples should be taken at the same time of day at all visits. Samples should be taken predose at Visits 2, 3, 4, 6, 7, 9, 11, 13 (or ED), 14, and 15. (revised per Amendments 02 and 03)

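### Table 5 footnote w ties the Visit 13 trough plasma sample, defined as predose, to a lumbar puncture set at 4 to 8 hours postdose

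*Protocol*

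**What the plan says.** Footnote w of Table 5 (current schedule, revised per Amendments 04 and 05) asks for two plasma PK samples at each PK visit. The first is "1 sample at predose (trough"). The order of events is explicit: "Instead, subjects will take the study drug at the clinic after collection of the predose PK sample". The second sample, which is 1 to 6 hours postdose at the other PK visits, becomes "another sample 4 to 8 hours postdose at Visit 13 (or ED") at the end of treatment.

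The same footnote adds, for the CSF substudy: "At Visit 13 (or ED), the trough PK blood sample should be collected shortly before or after completing the LP for subjects participating".

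Footnote y sets the conditions for the LP. The subject is dosed on site that day: "Visit 13 (or ED) also includes blood PK and PD assessments and so the subject will be dosed at the clinic on these days". The CSF timing follows: "A CSF sample will be collected by LP between 4 and 8 hours postdose". It must also match the time of day of the Screening LP to within 1 hour.

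**The concern.** Within one footnote, trough means before the dose; two sentences later the trough belongs next to a procedure that footnote y puts hours after the dose. A site coordinator who follows the substudy sentence as written collects, at about 4 to 8 hours postdose, a sample that is labelled trough.

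Two things are then at stake. The predose concentration at Visit 13 is missing, and a value from another part of the dosing interval stands in its place. Also, the sample whose window matches the LP, the 4 to 8 hour draw, has no instruction to be taken close to it. Section 9.7.1.7.2 plans to relate CSF biomarkers to plasma PK parameters and to CSF drug concentrations, so it needs to be known which plasma value belongs with which CSF value. The Core Study schedule has a single on-treatment CSF collection, at Visit 13 or ED, so the pairing cannot be recovered at a later treatment visit.

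**Working it through.** There is no sample size, power or alpha figure to reproduce. The check is interval arithmetic on the stated windows, with the clinic dose at t = 0.

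**Inputs**
- Trough (footnote w): predose, so t(trough) ≤ 0.
- LP (footnote y): 4 ≤ t(LP) ≤ 8 hours.
- Second PK sample at Visit 13 or ED (footnote w): 4 ≤ t(PK2) ≤ 8 hours.
- Substudy sentence (footnote w): t(trough) close to t(LP).

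**Step 1: gap between trough and LP.** t(LP) − t(trough) is at least 4 − 0 = 4 hours at the earliest permitted LP and at least 8 − 0 = 8 hours at the latest. The footnote does not define how close the draw must be. A gap of 4 hours or more is not a reasonable reading, because a separate sample already has the LP's own window.

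**Step 2: which instructions can hold together.**

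| Sequence on the day | Trough predose (w) | LP at 4 to 8 h (y) | Trough next to LP (w) |
|---|---|---|---|
| Predose draw, dose, LP and second draw at 4 to 8 h | yes | yes | no |
| Dose, then trough drawn at the LP | no | yes | yes |
| Predose draw with a predose LP | yes | no | yes |

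No sequence meets all three. Moving the LP to another day does not help, because it must still fall 4 to 8 hours after a dose.

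**Step 3: is there a spare sample?** Table 6 lists 7 PK time points and 14 collections of 2 mL: 7 visits × 2 samples = 14, and 14 × 2 mL = 28 mL. There is no third plasma sample at Visit 13. A trough drawn at the LP therefore replaces the predose sample, and both samples fall in or near the same 4 to 8 hour window.

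**Step 4: who is affected.** Only subjects given a dose that day. Footnote y provides for the other case: "If at an ED Visit, the subject has already stopped study drug, then no dosing will take place". With no dose, footnote w does not require a postdose sample, and a trough next to the LP contradicts nothing.

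**Step 5: how it probably arose.** The Amendment 04 text in the same file (Table 4, footnote w) reads: "At Visit 13 (or ED) the PK blood sample should be collected shortly before or after completing the LP for subjects participating". The word trough is absent there. Both that footnote and the Amendment 04 Section 9.5.1.4.1 link a trough to the LP directly after discussing substudy subjects who stopped drug before the ED visit. A change from superseded text is not itself an error, but it suggests that two sentences were condensed into one.

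**The case against.** The strongest reply is that one sentence is out of line and the rest of the schedule fixes the order. Footnote w defines trough and puts the dose after it. Footnote x asks for predose blood at Visit 13 for PD, so blood is being drawn then anyway. Footnote y fixes the dose and the LP. A sensible site draws predose, doses, then does the LP and the second draw at 4 to 8 hours. It departs from a single sentence and mistimes nothing. The second PK window was also set equal to the LP window, which is pairing of a loose kind. This stands as an account of what a careful site would do. It does not remove the contradiction, since that site has to set aside a written instruction.

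A reader might go further and infer that sites must mistime either the trough or the CSF sample. On that view, a site could do the LP before dosing, about 24 hours after the last once-daily dose. That is 24 − 8 = 16 to 24 − 4 = 20 hours away from the specified timing, and it would bias the CSF biomarker endpoints. The documents do not support this. Footnote w positions a blood draw relative to the LP and says nothing about when the LP occurs. Footnote y states the LP window outright, and no passage permits a predose LP in a dosed subject.

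The impact is also limited. The substudy is optional. Section 9.7.1.7.3 tests CSF biomarkers without multiplicity adjustment, outside the sequential procedure. The PK/PD work starts graphically. The population PK model in Section 9.7.1.7.1 can still use an off-trough sample if its true time is known. Finally, the Amendment 05 version of Section 9.5.1.4.1 is not in the part available and may be clearer. Table 5 would still contradict itself.

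**Conclusion.** The contradiction is certain as written. Footnote w conflicts with its own definition of trough and with footnote y for CSF substudy subjects dosed at Visit 13 or ED. Obeyed literally, it moves the sample labelled trough from predose to about 4 to 8 hours postdose and loses the predose level.

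The consequence is confined to plasma trough data and plasma-CSF pairing in an optional substudy. The share of subjects affected cannot be derived from the documents, because it depends on how many sites follow the outlying sentence. That every dosed substudy subject would be sampled wrongly is therefore not established. Nor is bias in the CSF biomarker endpoints. The primary CDR-SB analysis is untouched.

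This rests on two assumptions: that the LP is done after a clinic dose, as footnote y says, and that a draw close to the LP does not mean one 4 or more hours away. It is an inconsistency of wording and worth correcting, because the on-treatment LP is a single invasive procedure and its matching plasma value should not be left to interpretation.

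**What to change.** Reconcile footnotes w and y of Table 5, and align the current Section 9.5.1.4.1 and the laboratory manual with the result:

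- For subjects dosed at Visit 13 or ED, keep the trough as the predose draw and attach the LP-pairing instruction to the 4 to 8 hour postdose PK sample. This is consistent with the Amendment 04 sentence, which names only a PK blood sample.
- Keep a trough drawn with the LP only for ED subjects who have already stopped study drug.
- Record actual clock times of the dose, the LP and both plasma draws, so that any sample taken under the present wording can be placed correctly in the PK model.

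The cost is a footnote correction, a memo to substudy sites and, if they are not already captured, a few time fields. It adds no sample or procedure and leaves dosing and the LP window as the protocol states them.

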Day	1	15	29	57	85	183	274	365	456	547	638	729		757	813	
Week	1	3	5	9	13	27	40	53	66	79	92	105		109	117	
Weeks elapsed since 1st dose	0	2	4	8	12	26	39	52	65	78	91	104		108	116	
Nominal months elapsed since 1st dose	0		1	2	3	6	9	12	15	18	21	24		25	27	
Procedures/ Assessments																

- b: Subjects who discontinue taking study drug prematurely for any reason will undergo an ED Visit within 7 days of their last dose of study drug. In addition, Follow-up Visits will be scheduled 4 and 12 weeks after the last dose of study drug (Visit 14 and Visit 15, respectively). Subjects who discontinue study drug before reaching 12 months of treatment will also be asked to return to the clinic for a 12 month clinical assessment and then again at 24 months. Subjects who discontinue treatment between 12 and 24 months of treatment will be asked to return to the clinic for a 24 month clinical assessment. Subjects who discontinue early from study drug are considered “on study” as long as they continue to return for their clinical assessments at 12 and 24 months as outlined above, at which efficacy (MMSE, CDR, ADAS- cog14) and quality of life (EQ-5D, QOL-AD and Zarit’s Burden Interview) will be assessed along with concomitant medications. New AEs will be collected for 4 weeks post last dose and followed-up for 12 weeks, or until resolution, whichever comes first. If >4 weeks post last dose only AEs relating to study procedures will be collected. These 12 and 24 month clinical assessment visits do not need to be attended if they fall within 8 days (visit window) after the ED Visit or within ±8 days of either of the Follow-up Visits (Visit 14 and Visit 15).

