- c: All subjects, regardless of whether they complete all 24 months of treatment or discontinue study drug prematurely, will complete 2 posttreatment Follow-up Visits; one 4 weeks after the last dose of study drug and a second 12 weeks after the last dose of study drug (Visit 14 and Visit 15 respectively). If clinically indicated, more frequent safety assessments can be made as UNS assessments or visits during the posttreatment Follow-up Period. Subjects who have a Grade 2 or greater lymphocytopenia (less than 800/mm³) during the Follow-up Period (ie, at either Visit 14 or Visit 15) should have ALC measured every 4 weeks until resolution or confirmation of a non drug-related cause of the lymphocytopenia. ALC will be derived from the CBC with differential representing the normal lymphocytes (with atypical lymphocytes removed and presented as a separate count if they are present) and calculated by the white blood cell count × percentage of lymphocytes. Visit 15 will also act as Baseline for subjects who successfully complete the Core Study and will be enrolled into the open-label Extension Phase. (revised per Amendments 01 and 05)
- d: Unscheduled visits may be conducted at any time that additional assessments, including MRI scans, are clinically indicated in the judgment of the investigator. Note that not all assessments indicated under UNS Visits need be conducted – actual assessments needed will be determined by the investigator and will be based on the specific visit needs.
- e: Only if clinically significant abnormalities are found at Visit 14 and the investigator considers it necessary to repeat at Visit 15 or if the subject is continuing in the Extension Phase.
- f: Measurements of body temperature and sitting blood pressure and sitting heart rate will be obtained.

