- bb: The first dose of study drug will be given to the subject at the study site. Subjects will be encouraged to stay at the site for observation for at least 30 minutes following their first dose of study drug. The duration of this observation period can be extended at the investigator's discretion, eg, if warranted by medical history or concomitant medication. (revised per Amendment 03) Visit 2 bottles are re-dispensed at Visit 3 after accountability is performed. (revised per Amendment 05)
- cc: Only for Extension Phase subjects who did not participate in optional longitudinal substudies in the Core Study but who wish to consent to optional longitudinal substudies in the Extension Phase.
- dd: For subjects entering the Extension Phase only.
- ee: Immunological assessments only required for subjects randomized before 07 Sep 2018ff: New AEs will be collected for 4 weeks post last dose and followed-up for 12 weeks, or until resolution, whichever comes first. If >4 weeks post last dose, AEs relating to study procedures will be collected only
- gg: C-SSRS to be completed if any positive responses from the Clinical Assessment of Suicidal Thinking and Behavior
- hh: For those subjects entering the Extension Phase, NPI-12 will be used if available and both NPI-10 and NPI-12 scores calculated.
- ii: Not required for those entering Extension Phase

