9.5.4.1 Reporting of Serious Adverse Events

All SAEs, regardless of their relationship to study treatment, must be reported on a completed SAE form by email or fax as soon as possible but no later than 24 hours from when the investigator becomes aware of the event.

SAEs, regardless of causality assessment, must be collected up to 4 weeks after the last dose of study drug. All SAEs must be followed to resolution or, if resolution is unlikely, to stabilization. Any SAE judged by the investigator to be related to the study treatment or any protocol-required procedure should be reported to the sponsor regardless of the length of time that has passed since study completion. (revised per Amendment 05)

The detailed contact information for reporting of SAEs is provided in the Investigator Study File.

For urgent safety issues, please ensure all appropriate medical care is administered to the subject and contact the appropriate study team member listed in the Investigator Study File.

It is very important that the SAE report form be filled out as completely as possible at the time of the initial report. This includes the investigator's assessment of causality.

Any follow-up information received on SAEs should be forwarded within 1 business day of its receipt. If the follow-up information changes the investigator's assessment of causality, this should also be noted on the follow-up SAE form.

Preliminary SAE reports should be followed as soon as possible by detailed descriptions including copies of hospital case reports, autopsy reports, and other documents requested by the sponsor.

The investigator must notify his/her IRB/IEC of the occurrence of the SAE in writing, if required by their institution. A copy of this communication must be forwarded to the sponsor, or its designee, to be filed in the sponsor's Trial Master File.

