9.7.1.8.2 ADVERSE EVENTS

The AE verbatim descriptions (investigator terms from the eCRF) will be classified into standardized medical terminology using the Medical Dictionary for Regulatory Activities (MedDRA). AEs will be coded to the MedDRA (Version 19.0 or higher) lower level term closest to the verbatim term. The linked MedDRA PT and primary system organ class (SOC) are also captured in the database.

A TEAE is defined as:

- An AE that emerges on or after start of study treatment, having been absent at pretreatment (Baseline) or
- Reemerges on or after start of study treatment, having been present at pretreatment (Baseline) but stopped before treatment, or
- Worsens in severity on or after start of study treatment relative to the pretreatment state, when the AE is continuous. (revised per Amendment 03)

Only those AEs that are treatment-emergent will be included in summary tables. All AEs, treatment-emergent or otherwise, will be presented in subject data listings.

The TEAEs will be summarized by treatment group on the Safety Analysis Set. The incidence of TEAEs will be reported as the number (percentage) of subjects with TEAEs by SOC and PT. A subject will be counted only once within an SOC and PT, even if the subject experienced more than 1 TEAE within a specific SOC and PT. The number (percentage) of subjects with TEAEs will also be summarized by maximum severity (mild, moderate, or severe). The number (percentage) of subjects with TEAEs will also be summarized by relationship to study drug (Yes [related] and No [not related]).

The number (percentage) of subjects with treatment-related TEAEs will be summarized by SOC and PT. Treatment-related TEAEs include those events considered by the investigator to be related to study drug. The number (percentage) of subjects with treatment-related TEAEs will also be summarized by maximum severity (mild, moderate, or severe).

AEs will be summarized by the following subgroups: region, prior treatment with AChEIs or memantine (no or yes), and clinical subpopulation (MCI due to AD or the early stages of AD).

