1. Subjects who complete the 24-month Treatment Period and the 3-month Follow-up period (Visit 15) of the Core Study and whose Visit 15 falls within a 4-week window from the start of the Extension Phase. Subjects who discontinue study drug early are not considered to have ‘completed’ the Core Study.
2. Provide written informed consent. Subjects must, in the investigator’s judgment, have the capacity to consent (capacity to consent should be determined in accordance with applicable professional standards and local laws/regulations)
3. Subjects must continue to have an identified study partner who is willing and able to provide follow-up information on the subject throughout the course of the Extension Phase.

Study Design and Plan

The Extension Phase allows eligible subjects to receive elenbecestat 50 mg for up to 24 months (2 years), or until commercial availability of elenbecestat or a lack of positive benefit-risk is determined, whichever comes first.

Subjects who are enrolled and complete the Core Study, including the 3-month follow-up period, will have the option to participate in the Extension Phase. Subjects who discontinue from study drug during the Core Study are not eligible to participate in the Extension Phase.

Eligible subjects may enter the Extension Phase immediately following the completion of Core Study Visit 15. Subjects who are eligible to participate in the Extension Phase but who do not transition to the Extension Phase on the day of Visit 15 may enter the Extension Phase any time within 4 weeks of Visit 15. For all subjects, assessments performed at Visit 15 may serve as baseline values for the Extension Phase.

Subjects may discontinue from the open-label study drug for any reason but are required to complete the Early Discontinuation (ED) Visit (within 7 days of last dose). In addition, subjects are required to discontinue the open-label study drug if any of the criteria specified in [Section 9.3.3](#) (Removal of Subjects from Therapy or Assessment) are met.

Subjects who complete the Extension Phase treatment, or discontinue the study drug are required to complete the Follow-up Visit, 1 month after their last dose. The study will end when the last subject has completed the last Extension Phase study visit.

Treatment

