Safety analysis will be performed similarly to analyses in the Core Study. The Core Study baseline will be used for subjects who are randomized to elenbecestat initially, the Extension Phase baseline will be used for subjects who are randomized to placebo but receive elenbecestat during the Extension Phase. The incidence of AEs (including changes from baseline in physical and neurological examinations, and dermatological assessments), out-of-normal-range laboratory safety test variables, abnormal ECG findings, out-of-range vital signs, suicidality (C-SSRS), and changes from baseline in laboratory safety test variables, ECGs, safety MRI, vital sign measurements will be summarized by using descriptive statistics.

Efficacy Analyses

The following efficacy endpoints will be summarized by descriptive statistics and graphs:

- Changes from baseline in CDR-SB, ADCOMS, MMSE, FAQ, ADAS-cog14, and ADAS-cog14 Word List (immediate recall and delayed recall)
- Time to conversion to dementia for subjects who were not clinically staged as dementia based on clinical diagnosis at Core Study baseline based on clinical diagnosis
- Change from baseline in NPI-10 and NPI-12
- Proportion of subjects who receive increase and/or initiation of other AD pharmacotherapies

A delayed-start analysis ([Liu-Seifert et al, 2015](#)) will be performed for each efficacy endpoint at various scheduled visits in the Extension Phase. In addition, a mixed effects model for repeated measures (MMRM) will be used to analyze the above endpoints where appropriate.

Biomarker Analyses

The following biomarker endpoints will be summarized by descriptive statistics and graphs:

- Change from baseline in amyloid PET standardized uptake value ratio (SUVR)
- Change from baseline in tau PET signal
- Change from baseline in total hippocampal volume as measured by vMRI
- Change from baseline in the preservation of connectivity as measured by fMRI

- Change from baseline in t-tau, p-tau, A β (1-42) and A β (1-x) in CSF
- Change from baseline A β (1-x) in plasma
- Change from baseline in exploratory biomarkers eg, NFL, VILIP1, YKL-40, and Ng in CSF and plasma

A delayed-start analysis and MMRM model will be used to analyze these biomarker endpoints.

The relationship between efficacy endpoints and biomarker endpoints will be explored using correlation analysis.

Sample Size Rationale

Not applicable.

Table 9 Schedule of Procedures/Assessments in Extension Phase

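### New adverse events stop being collected 4 weeks after the last Core dose, but Visit 15 at week 12 is the baseline for judging former-placebo subjects' Extension TEAEs, so conditions arising in between have no recorded onset or severity

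*Protocol*

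**What the plan says.** The current text (Amendment 05) sets the AE window in two footnotes to the Table 5 schedule. Footnote ff, attached to the adverse-event row, reads: "New AEs will be collected for 4 weeks post last dose and followed-up for 12 weeks, or until resolution, whichever comes first". It then adds: "If >4 weeks post last dose, AEs relating to study procedures will be collected only". Footnote b gives the same rule for subjects who stop early: "If >4 weeks post last dose only AEs relating to study procedures will be collected". Section 9.5.4.1 matches it for serious events: "SAEs, regardless of causality assessment, must be collected up to 4 weeks after the last dose of study drug". The same paragraph keeps SAEs judged related to treatment or a protocol-required procedure reportable at any later time.

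Footnote c to Table 5 places Visits 14 and 15 at 4 and 12 weeks after the last dose and states that "Visit 15 will also act as Baseline for subjects who successfully complete the Core Study" and go on to the open-label Extension. Appendix 5 lets subjects who do not cross over on the day start later: they "may enter the Extension Phase any time within 4 weeks of Visit 15". For the Extension safety analysis, Appendix 5 says "the Extension Phase baseline will be used for subjects who are randomized to placebo but receive elenbecestat during the Extension Phase". That analysis is to be done as in the Core Study. There, Section 9.7.1.8.2 defines a TEAE as an event absent at baseline that emerges on treatment, one that had stopped and re-emerges, or one that worsens "relative to the pretreatment state, when the AE is continuous".

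**The concern.** All three limbs of the TEAE definition need to know which conditions the subject had just before treatment, and how severe they were. For former-placebo subjects that reference point is Visit 15, but by then the protocol has not been recording new non-procedure events for eight weeks. Table 5 has no medical-history row; medical history is taken only at Screening (Table 4). If a condition began in those weeks and is still present when open-label drug starts, the database cannot separate a condition continuing unchanged (not a TEAE) from a new or worsened one (a TEAE).

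Long-term safety is the Extension's primary objective, AEs are the first-listed component of its primary endpoint, and former-placebo subjects supply its first-exposure data. Pre-existing conditions logged as new would inflate the event count in that group.

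**Working it through.** **Inputs from the protocol.** Table 5 day row: Visit 13 (end of treatment) Day 729, Visit 14 Day 757, Visit 15 Day 813. Entry delay in Appendix 5: up to 4 weeks (28 days) after Visit 15. Section 9.7.2: 950 subjects per arm across the two studies, 30% dropout.

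**Visit timing, reproducing the protocol's own figures.**
- Visit 14: (757 − 729) / 7 = 4.0 weeks after end of treatment.
- Visit 15: (813 − 729) / 7 = 12.0 weeks.

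Both agree with footnote c.

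**Length of the gap.**
- Visit 14 to Visit 15: 813 − 757 = 56 days, out of 813 − 729 = 84 days. 56 / 84 = 67%.
- With entry at the end of the 4-week window: (56 + 28) / (84 + 28) = 84 / 112 = 75%.
- A late entrant also has no scheduled AE check between Visit 15 and Visit 16 (Extension Day 15), the first column of Table 9.

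**Subjects potentially affected.** 950 × (1 − 0.30) = 665 former-placebo subjects at most, both studies together. This takes every subject who does not drop out as entering; subjects who stopped drug early are not eligible.

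**Illustrative size.** The protocol gives no AE rate and no fraction continuing. Assume 1 to 2 new AEs per subject-year, with 20% to 40% continuing when the Extension starts. Conditions per subject = rate × 8/52 × fraction continuing.

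| Case | Calculation | Per 1,000 entrants | Of 665 |
|---|---|---|---|
| Low | 1 × 8/52 × 0.20 = 0.031 | 31 | 20 |
| Middle | 1.5 × 8/52 × 0.30 = 0.069 | 69 | 46 |
| High | 2 × 8/52 × 0.40 = 0.123 | 123 | 82 |

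These are expected numbers of unrecorded continuing conditions. A subject with two is counted twice, so the number of subjects is slightly lower. They are not counts of misclassified TEAEs: a condition that truly worsens on drug is a TEAE either way, and one whose earlier onset is correctly elicited later would not be counted as emerging. The protocol gives no basis for estimating the fraction that would be misclassified.

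**The case against.** The strongest reply is that much of the pretreatment state is recorded. Extension entrants have physical and dermatologic examination, vital signs, weight, ECG, laboratory tests, urinalysis, C-SSRS and a full neurologic examination at Visit 15, and concomitant medications are noted. Appendix 5 calls Visit 15 Day 1 of the Extension and says that all AEs and SAEs are recorded, and the AE row is marked at that visit. Extension safety results are descriptive, and no Core comparison is affected. The current version of Section 9.5.1.5.1, which deals with AE collection, is not in the file.

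Part of this stands. The Visit 15 baselines for laboratory, ECG, vital-sign, examination and suicidality endpoints are sound, so a reader should not infer that the Extension's whole primary safety objective rests on an unrecorded state. Nor should a reader infer that the off-drug interval is lost for seeing whether on-drug events stop: events begun by week 4 are followed to week 12 or resolution. Not all late SAEs are lost either, since related ones stay reportable.

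The rest does not close the gap. One-day examinations and a medication list do not give onset and severity of symptomatic or episodic events. The general statement in Appendix 5 does not override the explicit footnote attached to the AE row; at best the two conflict. The text elsewhere in the file that collects AEs through Visit 15 and SAEs for 12 weeks (Sections 9.5.1.5.1 and 9.5.4.1 of the earlier protocol version) is superseded.

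**Conclusion.** The point holds, confined to AE and TEAE classification in former-placebo subjects entering the Extension. Followed as written, the protocol leaves 56 of the 84 days before Visit 15 (67%), and up to 84 of 112 days before the first open-label dose (75%), without collection of new non-procedure AEs or of SAEs not judged related. Those lengths follow directly from the protocol. The figure of about 31 to 123 unrecorded continuing conditions per 1,000 entrants over the 8 weeks (about 20 to 82 among at most 665) depends on assumed AE rates and continuing fractions, and only some of these conditions would lead to a wrong classification. The likely direction is over-counting, because unchanged conditions may be logged as new. The effect is moderate, but the change is worth making before subjects pass Visit 15, since onset and severity are hard to recover afterwards.

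**What to change.** In Table 5 footnotes b and ff and in Section 9.5.4.1, reconcile the collection window with Appendix 5 by adding that, for subjects entering the Extension, all AEs and SAEs with onset since the last Core dose are recorded at Visit 15 with onset, severity and whether continuing, and that collection then runs on to the first open-label dose. State in the Appendix 5 safety analysis that this record is the pretreatment state for Extension TEAEs in subjects randomized to placebo.

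The cost is an amendment sentence in each place. Visit 15 already has an AE check, so no visit or procedure is added. The downside is extra AE entries, some relying on recall over 8 weeks.
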